1.0 Background & Rationale

Neonatal abstinence syndrome (NAS) is a pattern of withdrawal symptoms seen in newborn infants who are exposed to opioids in utero. The incidence of this condition has increased drastically over the last two decades as a result of the ongoing nationwide opioid epidemic.¹⁻³ In 2015, the NICU at Indiana University Health Methodist Hospital implemented a guideline for the management of NAS. This guideline includes the modified Finnegan scoring tool to assess severity of withdrawal symptoms and guide interventions, particularly when it is appropriate to initiate pharmacologic treatment. This guideline was successful in reducing the mean length of stay for infants treated for NAS from 27.7 days to 19.7 days. However, the average length of stay has remained stable since then and concerns have been raised that we may be treating infants too aggressively based on this guideline. In 2018, a total of 154 infants (\geq 35 weeks gestation) with intrauterine opioid exposure were born at IU Health Methodist Hospital. Of these infants, 43% (66 infants) required treatment with morphine with an average length of stay of 21.5 days.

Currently there is no uniformly accepted treatment strategy for NAS and both the choice of primary medication and criteria for treatment vary widely.^{4,5} Morphine is by far the most commonly used medication for NAS treatment, followed by methadone.^{6,7} Buprenorphine is also gaining interest and appears to be a viable option for treatment of NAS in terms of safety and feasibility of dosing.⁸ Based on a small number of randomized trials and retrospective cohort studies, it appears to be superior in terms of length of treatment in comparison to methadone and morphine.⁸⁻¹⁰ However, there is still a need for larger scale studies. In neonates, buprenorphine is administered sublingually in a solution of 30% ethanol and is not as readily available in this form. The question of which medication is optimal to treat NAS is highly debated. Many studies seeking to answer this question have been published, but due to variability of multiple factors and overall low quality of evidence, it is difficult to come to a single conclusion regarding appropriate medication choice and dosing schedule.¹⁰ We have chosen to use morphine as it is readily available, has been used widely in newborns, and has a shorter half-life which makes it easier to titrate dosing quickly for symptom management.

The starting dose of morphine and protocols for adjusting the dose are variable as well. In general, most institutions use a starting dose of 0.04 – 0.05 mg/kg of morphine given every 3-4 hours. Our current practice is to use 0.05 mg/kg every 3 hours and to increase the dose as needed based on response, measured by the modified Finnegan score. Once an infant is stable for 48 hours on a particular dose, the weaning phase is initiated. A stable condition is defined as a modified Finnegan score less than 9, eating well, gaining weight and sleeping. However, Grossman et al had success in decreasing the length of stay for infants with NAS using intermittent/as needed morphine dosing in combination with a novel approach to scoring.¹¹ In this model, infants are monitored with a scoring system and a dose of morphine is only given if the infant meets specified criteria for treatment, with a minimum interval of 3 hours between

doses. While this is promising, there have been no studies thus far comparing as-needed morphine dosing to the current standard approach of scheduled dosing with gradual weaning of the dose. This is an important piece of information as many centers are seeking to adopt this method without the supporting evidence of a randomized trial.

2.0 Objective(s)

- **2.1 Primary Objective:** To evaluate the feasibility of conducting a randomized controlled trial by examining enrollment.
- **2.2 Secondary Objective:** To evaluate the feasibility of conducting a randomized trial by identifying any concerns related to the practicality of the study protocol.
- **2.3 Tertiary Objective:** To provide an estimate of means and standard deviations necessary to conduct a definitive RCT.

3.0 Outcome Measures/Endpoints

- **3.1** Primary Outcome Measure: Enrollment rate, drop out rate, number of patients switched to standard arm
- **3.2 Secondary Outcome Measure:** Length of hospital stay from birth to discharge,
- **3.3** Total cumulative morphine exposure (per kilogram of body weight), peak morphine dose, and length of morphine treatment (in days)

4.0 Eligibility Criteria

4.1 Inclusion Criteria

- Neonates \geq 35 weeks gestation with intrauterine opioid exposure
- Severe NAS (modified Finnegan score \geq 9) requiring NICU admission

4.2 Exclusion Criteria

- Infants with significant co-morbidities requiring analgesia or sedation due to clinical condition
- Infants with ongoing need for respiratory support
- Infants with suspected genetic abnormalities or significant congenital anomalies that would interfere with accurate modified Finnegan scoring or response to oral morphine
 - Mother and baby pairs in which the mother is under the age of 18 years old

5.0 Study Design

This will be a pragmatic pilot randomized controlled trial comparing scheduled versus intermittent morphine dosing for severe neonatal abstinence syndrome, performed in the Riley Hospital for Children Neonatal Intensive Care Unit (NICU) at IU Health Methodist Hospital. In 2018, 154 babies admitted to IU Health Methodist were exposed to opioids in utero. [name] has clinically treated and conducted research with this population since 2015. We hypothesize that treating NAS symptoms on an as-needed basis will result in decreased use of morphine and decreased length of stay. Severity of NAS will be defined by the modified Finnegan scoring tool, which is already in use.¹² This tool is administered by the bedside nurse

every 3-4 hours and uses graduated scoring of 21 items which are then added together to give the modified Finnegan score.

The current guideline for pharmacologic treatment of neonatal abstinence syndrome uses the modified Finnegan score to determine the severity of symptoms. Modified Finnegan scoring should be performed every 3 hours after a feeding. If an infant reaches the threshold score for treatment (\geq 9), morphine is initiated at 0.05 mg/kg/dose orally every 3 hours. If the modified Finnegan score continues to be elevated, the dose is escalated per a protocol until the modified Finnegan score is in an acceptable range. Once the infant's modified Finnegan score has been stable for at least 48 hours on a particular morphine dose, the weaning phase begins. Morphine is weaned by 10% of the peak dose every 24 hours as tolerated based on symptoms. When the dose has been weaned to < 0.02 mg/kg/dose, it may be discontinued. In order to be discharged home from the hospital, the infant needs to remain stable off of morphine for at least 48 hours. The study group will also be assessed using the modified Finnegan scoring tool. These infants will receive morphine at the same starting dose of 0.05 mg/kg/dose but on an asneeded basis as often as every 3 hours if the modified Finnegan score reaches the threshold for treatment. Our goal is to enroll 24 participants with 12 patients on each arm. A success rate would be a retention of 80% (approximately 20 participants).

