 - b. The infant will then receive 0.075 mg/kg dose when indicated.
 - c. The morphine dose may be escalated to 0.1 mg/kg if the infant receives 3 consecutive doses of 0.075 mg/kg and again qualifies for a 4th consecutive dose
 - d. If it has been more than 24 hours since the previous dose of morphine and the infant again qualifies for a dose, it will be decreased back to the lower dose
- 4. If an infant receives all 8 possible doses of morphine within a 24-hour period (i.e. the infant receives morphine every 3 hours for 24 hours consecutively), the infant will be removed from the study protocol and placed on morphine per the standard guideline
- 5. An infant will be eligible for potential discharge once they have been stable for 48 hours without receiving a dose of morphine.

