8.0 Study Calendar

Timeline	Birth	Admission to NICU	Treatment	Discharge	Follow-up
Study Procedures	Screening for potential eligibility based on opioid exposure	Determine eligibility and approach for enrollment	Follow treatment course	Final data collection on outcomes	Phone call/chart review) at 4-8 weeks of age to assess for re- admission
		Collect baseline maternal and newborn data	Monitor for protocol deviations, issues, AEs, SAEs	Confirm contact information for follow-up phone call	
		Randomize	Continue data collection		

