11.0 Study Withdrawal/Discontinuation

Infants may be withdrawn from the study at any time at the request of the parent(s). If withdrawn from the study, they will receive standard treatment for neonatal abstinence syndrome, consistent with the control group. Infants may also be withdrawn from the study if there is a change in clinical status rendering it necessary to deviate from the study protocol per physician discretion.

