15.0 Follow-up and Record Retention

The duration of the study will from be from enrollment through 4-8 weeks of age. The majority of the data collection and monitoring will be done during the initial hospital stay. Once the infant is discharged from the NICU, we plan to contact the parent via phone for follow-up to determine if the infant has required readmission to the hospital for any issues potentially related to neonatal abstinence syndrome in the first month of life. If the baby stays in the IU Hospital system after birth, the study team will look for recent appointments that may contain the follow up information.

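### Does the pilot's one success benchmark, 80% pooled retention, need a fuller definition and companion thresholds for enrollment and switching?

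*Combined protocol and SAP*

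**What the plan says.** The primary objective in section 2.0 is "To evaluate the feasibility of conducting a randomized controlled trial by examining enrollment". Section 3.0 lists three primary outcomes: "Enrollment rate, drop out rate, number of patients switched to standard arm". None of them has a threshold.

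Section 5.0 sets the size ("Our goal is to enroll 24 participants with 12 patients on each arm") and the only benchmark ("A success rate would be a retention of 80% (approximately 20 participants"). Section 12.0 adds no feasibility criterion. It justifies 12 per group as a size suggested for pilot studies.

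Two places bear on what happens to a switched infant. Under item 4 for the study group in section 7.0, an as-needed infant who receives every possible dose over 24 hours is switched: "the infant will be removed from the study protocol and placed on morphine per the standard guideline". Section 11.0 separately allows withdrawal at the parents' request, or after a "change in clinical status rendering it necessary to deviate from the study protocol per physician discretion".

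Two places bear on timing. The discharge column of the section 8.0 calendar reads "Final data collection on outcomes". Section 15.0 says "The duration of the study will from be from enrollment through 4-8 weeks of age", with a phone call or record check for readmission.

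**The concern.** A pilot whose purpose is feasibility should have a benchmark that can be read in only one way, and this one leaves three things open.

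- **Switching.** Section 3.0 lists drop-out and switching as separate items, which suggests that a switched infant is still retained. If so, every as-needed infant could end up on the control regimen and the pilot would score full retention. The removal wording in section 7.0 and the physician withdrawal in section 11.0 support the opposite reading.
- **Time point.** Retention to discharge and retention to the 4-8 week contact could differ, and neither is named.
- **Enrollment.** The primary objective is enrollment, but the benchmark concerns retention. The goal of 24 is a count, with no denominator and no accrual period.

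At stake is whether the designers of the larger trial could be misled by a feasibility verdict that hides heavy crossover or slow recruitment.

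**Working it through.** **1. The plan's own figure.** 0.80 x 24 = 19.2, which rounds up to 20. 20/24 = 83.3% meets 80%; 19/24 = 79.2% just misses it. One arm alone would give 0.80 x 12 = 9.6, so the stated count of about 20 fits only the pooled total.

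**2. Two readings of a switch.** Let s be the number of as-needed infants switched, with nobody else lost.

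| s | Switch counts as retained | Switch counts as lost: (24 - s)/24 |
|---|---|---|
| 4 | 24/24 | 20/24 = 83.3% |
| 5 | 24/24 | 19/24 = 79.2% |
| 12 | 24/24 | 12/24 = 50% |

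The readings agree on the verdict while losses and switches together total 4 or fewer.

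**3. How often the reading would matter.** The documents give no switch or loss rate, so both are assumed here. If a switch is a loss, each control infant is retained with probability 1 - loss and each as-needed infant with probability (1 - loss) x (1 - switch rate). Adding two binomials of size 12 gives the chance of meeting the cut.

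| Switch rate | 20 or more, loss 0% | 20 or more, loss 5% | 20 or more, loss 10% | 19 or more, loss 5% |
|---|---|---|---|---|
| 10% | 99.6% | 92% | 74% | 98% |
| 20% | 93% | 74% | 51% | 89% |
| 1/3 | 63% | 41% | 23% | 62% |
| 1/2 | 19% | 10% | 5% | 23% |
| Switch counts as retained (any rate) | 100% | 99% | 91% | 99.9% |

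At 5% other loss the definition matters little at 10% switching, and clearly from about 20% upward.

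**4. Can a reader recover the answer?** Yes. Section 3.0 makes drop-out and number switched primary outcomes in their own right. With 24 randomized, d dropped out and s switched (no infant in both groups), retention is (24 - d)/24 on one reading and (24 - d - s)/24 on the other. A pilot in which all 12 switched would have to report 12 switches as a primary result.

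**5. Time point.** The outcomes in section 3.0 concern recruitment, staying in the study, switching, length of stay and morphine exposure. Section 8.0 closes outcome collection at discharge. The later contact looks for readmission, which section 3.0 does not list, and it may be done by chart review. Discharge is therefore the reading that fits the outcomes.

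**6. Enrollment.** The only volume figure is the 66 morphine-treated infants in 2018 (section 1.0). It is a stand-in for the eligible number, because eligibility rests on score and NICU admission, less exclusions. Under assumed accrual times, 24 enrolled would be 24/33 = 73% in six months, 24/66 = 36% in one year and 24/132 = 18% in two. This shows that a count is not a rate. It does not show that the rate will go unreported, because enrollment rate is the first primary outcome listed.

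**7. Would added thresholds help?** Exact 95% intervals are 62.6% to 95.3% for 20/24 and 10% to 65% for 4/12. At a true retention of 80%, the chance of 20 or more of 24 is 46%, and of 19 or more 66%. Cut-offs at this size separate good from poor feasibility only weakly.

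**The case for a change.** The strongest case for a change is that feasibility is the whole purpose of this pilot. Its one benchmark can score the same data as 100% or as 50%, and a few sentences of definition would cost no infants and no visits. Monthly monitoring of recruitment and retention (sections 10.0 and 13.0) supplies no definition either. An enrollment rate also needs a denominator, and a log of eligible infants not enrolled is easier to keep from the start than to rebuild.

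Much of this stands as description. The benchmark is undefined as to switching and time point, and enrollment rate has no stated denominator. A careful report should say which convention it used: retention to discharge whatever the treatment received, shown by arm; switching over the 12 as-needed infants; and enrollment over eligible infants.

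What does not stand is the step from there to a defect in the plan. The claim that all 12 could switch and still pass holds on only one of two arguable readings. Whichever is adopted, the switches are reported as a primary outcome. Screening for opioid exposure from birth is already planned, so the information for a denominator can be gathered. A threshold for each feasibility outcome is a debatable preference at this size, and the documents give no values to base one on.

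**Conclusion.** The concern identifies missing detail, not an error that calls for a change. The arithmetic is sound: the benchmark is pooled, and its verdict can turn on how switches are counted once switches and losses exceed 4 of 24. The consequence is small. All three primary outcomes are reported separately, discharge is the natural time point, and no hypothesis test, sample size or progression decision is tied to the 80%. An analyst would report the component counts and state the convention, and either version of retention follows from them. Guide values for switching or enrollment would add little, given an interval of 10% to 65% for 4 of 12.

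This rests on drop-outs and switches being reported as distinct counts, as section 3.0 sets out, and on the benchmark remaining descriptive. The switch, loss and accrual figures used above are assumptions.

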6.0 Enrollment/Randomization

Patients will be assessed for eligibility at the time of birth based on known intrauterine opioid exposure. The parents will not be approached for participation in the study unless the infant is admitted to the NICU with severe NAS symptoms. If eligible, the mother will be approached for informed consent upon admission to the NICU or, if already admitted to the NICU, upon recognition that the infant has severe symptoms that may need morphine. Once consent has been obtained, the infant will be randomized via paper process that has been designed by a biostatistician in block sizes of 4-6 patients with a 1:1 ratio. Randomization can occur after the first dose of morphine as the second dose of morphine is considered a study procedure.

7.0 Study Procedures

Newborns will be screened for enrollment if they are exposed to opioids in utero. We will not approach the parents of infants with opioid withdrawal if they are stable and remain in the well newborn nursery. Once the newborn is enrolled and randomized prior to the second dose of morphine they will continue to be monitored per standard care with the modified Finnegan score. Information will be collected from the mother's medical chart, including her age, medical problems, Hepatitis C status, labor and delivery complications, prior history of drug use, current medications, prenatal screening labs, and urine toxicology results. Information will also be collected from the newborn's chart, including gestational age at birth, mode of delivery, Apgar scores, birth weight, modified Finnegan scores, length of time in the newborn nursery prior to NICU admission, nutrition (breastfeeding vs formula), urine, meconium, and umbilical cord toxicology screens.

All infants will receive optimal non-pharmacologic interventions per standard care, such as parental rooming-in when possible, breastfeeding when possible, quiet and dimly-lit environment with low stimulation, close contact with caregiver for soothing, pacifier, and on-demand feedings.

Each group will be monitored with the use of the modified Finnegan score to quantify the severity of NAS, per the current standard care. **It is performed by the bedside nurse every 3-4 hours following a feeding**. Due to the pragmatic nature of this pilot trial, FINN scores obtained outside this window will not be a deviation. Bedside nursing is trained in the modified Finnegan scoring process. If a patient meets the threshold for morphine (modified Finnegan score ≥ 9 , or a score of ≥ 12), a second nurse should immediately perform a separate score to confirm. The threshold for initial dose of morphine will be the same for both the standard care control and the study group. All infants with intrauterine opioid exposure will remain inpatient for observation for a minimum of 5 days before discharge, per standard care. The details of treatment for each group are outlined below.

Standard Care (Control) Group

- 1. Initiation of morphine and stabilization
 - a. Non-pharmacologic care (infant soothing techniques) should be optimized prior to initiating morphine or increasing the dose. If the clinical team feels non-pharmacologic care has not been optimized, it is appropriate to do so and re-evaluate the next modified Finnegan score before initiating or increasing morphine.
 - b. Treatment should be initiated if an infant has **two** consecutive modified Finnegan scores \geq 9 or one score \geq 12.
 - i. Initial dose: morphine 0.05 mg/kg/dose every 3 hours.
 - c. Modified Finnegan scoring will continue every 3 hours.
 - i. If the infant's modified Finnegan score remains ≥ 12 , a rescue dose of double the previous dose should be given. For instance, if an infant is given 0.05 mg/kg/dose and the next modified Finnegan score is ≥ 12 , a rescue dose of 0.1 mg/kg/dose should be given x1.
 - ii. If the modified Finnegan score is < 12 after the rescue dose is given, that dose should be given as the maintenance dose every 3 hours.

- iii. If the modified Finnegan score remains > 8 but < 12, escalate the morphine dose by 0.03 mg/kg/dose every 3 hours until the scores are \leq 8.
- iv. Before increasing the dose, ensure that there has been sufficient time to observe the patient's response to the previous dose given. For example, if an infant receives a morphine dose at the time of a feeding, the Finnegan score is then assigned 1 hour after the feeding. This is not sufficient time to reflect the response to the most recent morphine dose. There should be a full period of observation (at least 2 hours) after a dose before a decision is made to escalate the dose.
- d. Once the modified Finnegan scores are consistently ≤ 8 , continue the maintenance dose for 48 hours before beginning the weaning phase.
- e. If the morphine dose exceeds 0.3 mg/kg/dose, consider adding phenobarbital as an adjunctive medication.
 - i. Loading dose: phenobarbital 10 mg/kg/dose q12 hours x2 doses
 - ii. Maintenance: phenobarbital 5 mg/kg/dose q24 hours
- 2. Weaning
 - a. Once the infant has been stable for 48 hours, begin weaning the dose of morphine by 10% of the original maintenance dose (the dose on which the infant has been stable) every 24 hours. For example, if the maintenance dose is 0.05 mg/kg/dose, each wean should decrease by 10% of that dose = 0.005 mg/kg/dose.

i. Maintain the dosing interval of every 3 hours throughout the entire weaning process.

- b. If the infant has two consecutive modified Finnegan scores ≥ 9, increase back to the previous dose at which the infant was stable.
 - i. If modified Finnegan scores continue to be > 8 after going back to the previous dose, continue to increase the dose in a stepwise fashion. Consider weight-adjusting the dose if appropriate.
 - ii. Remember to optimize non-pharmacologic measures and rule out other causes of agitation before increasing the dose.
- c. Once the infant is stable again for 48 hours, resume weaning by 10% of the original maintenance dose.
- d. Once a single dose is < 0.02 mg/kg, discontinue morphine.
- e. If the infant is receiving phenobarbital, discontinue at second to last step of morphine wean.
- f. Infants should be monitored for a minimum of 48 hours after discontinuing morphine prior to discharge.
- g. If the infant qualifies for treatment based on modified Finnegan scoring AFTER discontinuation of morphine, restart morphine at the previous dose at which the infant was stable (the ending dose of the weaning schedule).
 - i. Once infant is stable for 48 hours, consider weaning an additional step prior to discontinuing morphine.
 - ii. If the infant meets criteria for a rescue dose, give a one-time dose of double the previous dose at which infant was stable.

i. For example, if the previous dose at which the infant was stable was 0.07 mg, give 0.14 mg x1 and resume the maintenance dose at 0.07 mg. Do not use 0.14 mg as the new maintenance dose unless infant requires a repeat rescue dose.

Study Group

- 1. Non-pharmacologic care (infant soothing techniques) should be optimized prior to giving a morphine dose. If the clinical team feels non-pharmacologic care has not been optimized, it is appropriate to do so and re-evaluate the next Finnegan score before giving morphine.
- 2. If the modified Finnegan score is ≥ 9 for **two** consecutive scores or ≥ 12 for one score, the infant will be given a one time dose of 0.05 mg/kg of morphine orally.
- If any subsequent modified Finnegan score is ≥ 9, the infant may receive a repeat dose of morphine 0.05 mg/kg. Before repeating a dose, there should be an adequate period of observation after the prior dose was given (at least 2 hours) for the Finnegan score to reflect the response to a dose.
 - a. If an infant has received 3 consecutive doses of 0.05 mg/kg/dose every 3 hours and continues to qualify for a 4th dose consecutively, that dose will be increased to 0.075 mg/kg/dose
 - b. The infant will then receive 0.075 mg/kg dose when indicated.
 - c. The morphine dose may be escalated to 0.1 mg/kg if the infant receives 3 consecutive doses of 0.075 mg/kg and again qualifies for a 4th consecutive dose
 - d. If it has been more than 24 hours since the previous dose of morphine and the infant again qualifies for a dose, it will be decreased back to the lower dose
- 4. If an infant receives all 8 possible doses of morphine within a 24-hour period (i.e. the infant receives morphine every 3 hours for 24 hours consecutively), the infant will be removed from the study protocol and placed on morphine per the standard guideline
- 5. An infant will be eligible for potential discharge once they have been stable for 48 hours without receiving a dose of morphine.

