Grade 4: Life-threatening consequences; coma; urgent intervention indicated Grade 5: Death

- 2. Other events classified as serious and unexpected
- 3. Other events resulting in death or classified as Serious or Related (to study procedures)

A depressed level of consciousness grades 1-3 will be considered an AE, while grade 4 will be considered a SAE. All SAEs and AEs reported during this study will be followed until resolution or until the investigator confirms that the AE/SAE has stabilized and no more follow-up is required. All deaths and SAEs that are at least possibly related and all unexpected SAEs will be

reported to the investigator within 24 hours of the study team becoming aware. An initial SAE form must be as complete as possible, including details of the current serious adverse event, including an investigator assessment of the causal relationship between the event and study procedures. Information not available at the time of the initial report must be documented on a follow-up SAE form. All unexpected SAEs will be reported to the IRB within 5 working days. The study team will begin tracking AEs and SAEs at the time of consent and will conclude tracking after the follow-up phone call has been made when the infant is 4-8 weeks of age.

We will not report deviations as clinical care is being followed. This is a pragmatic pilot trial that is not intended to alter the standard of care treatment. It is ideal that the morphine is dosed every 3 hours/FINN scores obtained for those on the standard arm. However, there will be times this does not occur, and it will not be considered a protocol deviation.

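### The study-arm switch rule assumes a dose every 3 hours while study infants may be scored every 3-4 hours, so the number switched (a primary component) depends partly on scoring interval; how switched infants count towards retention is also unstated

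*Combined protocol and SAP*

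**What the plan says.** **The trigger.** Section 7.0, Study Group item 4, reads: "If an infant receives all 8 possible doses of morphine within a 24-hour period (i.e. the infant receives morphine every 3 hours", and continues that this lasts 24 hours without a break. The infant then leaves the study protocol and is treated under the standard guideline. Item 3a, on dose escalation, also describes consecutive doses as 3 hours apart.

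**The scoring interval.** Earlier in Section 7.0: "Each group will be monitored with the use of the modified Finnegan score". The scoring is "performed by the bedside nurse every 3-4 hours following a feeding", and "FINN scores obtained outside this window will not be a deviation". Section 5.0 also gives 3-4 hours when it introduces the tool. A fixed 3-hour scoring interval appears in two places only: the description of the current guideline in Section 5.0 ("Modified Finnegan scoring should be performed every 3 hours after a feeding") and the control-group steps in Section 7.0, item 1c ("Modified Finnegan scoring will continue every 3 hours"). The study-group steps give no scoring interval. Section 5.0 caps study-arm dosing at once every 3 hours, subject to a qualifying score.

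**Deviations.** Section 9.0 says "It is ideal that the morphine is dosed every 3 hours/FINN scores obtained for those on the standard arm", which concerns the control group, and "We will not report deviations as clinical care is being followed".

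**Outcomes.** Section 3.1 lists three primary components: enrollment rate, drop out rate, and the number of patients switched to the standard arm. Section 5.0 sets success at 80% retention, about 20 of 24. Section 11.0 allows withdrawal by parents or at physician discretion; for parental withdrawal it specifies treatment consistent with the control group.

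**The concern.** A study infant is dosed only after a qualifying score, so the number of doses possible in a day is limited by how often the infant is scored. Item 4 takes that number to be eight. Under the scoring interval that Section 7.0 allows, it can be lower. Two infants who qualify at every score can then differ in whether and when they are counted as switched, because of scoring interval and not response. This pilot exists to inform a larger trial, and the number switched is one of the feasibility figures it would pass on.

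A second, related gap concerns labels. Retention is the only stated success criterion, and the plan does not say whether an infant moved under item 4, or moved at physician discretion under Section 11.0, is switched, dropped out or retained. If switches counted as lost, longer scoring intervals would also make retention look better.

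**Working it through.** **1. The plan's own figure.** At 3-hour intervals 24/3 = 8 doses, at 0, 3, ..., 21 h. This reproduces item 4. A dose at exactly 24 h would be a ninth, so eight as the maximum fits best if that dose is left out of the window.

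**2. The same count at 4 hours.** 24/4 = 6 doses, or 7 if a dose at exactly 24 h is included. Eight doses span seven gaps, and 7 × 4 = 28 h. The rule cannot fire under any reading.

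**3. Mixed gaps.** With k gaps of 4 h among the seven, and the rest 3 h, eight doses span 21 + k hours.

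| k | Span (h) | Under 24 h | At most 24 h | Every 3 hours, literally |
|---|---|---|---|---|
| 0 | 21 | fires | fires | fires |
| 1 | 22 | fires | fires | no |
| 2 | 23 | fires | fires | no |
| 3 | 24 | no | fires | no |
| 4 to 7 | 25 to 28 | no | no | no |

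The two halves of item 4 therefore disagree. Eight doses in 24 hours tolerates two 4-hour gaps (three if exactly 24 h counts); the every-3-hours explanation tolerates none. For a repeating pattern of 4, 4, 3 h, every run of seven gaps holds at least four of 4 h, so the rule never fires.

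**4. Illustration.** Assumptions, none of them from the documents: every score leads to a dose, and each gap is independently 4 h with probability q, otherwise 3 h. By 24 h only the first seven gaps matter, so the chance of firing is a binomial probability. At q = 0.5:

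- under 24 h: P(k ≤ 2) = (1 + 7 + 21)/128 = 22.7%
- at most 24 h: P(k ≤ 3) = 64/128 = 50.0%
- literal 3-hour reading: P(k = 0) = 1/128 = 0.8%

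An exact recursion over the running last seven gaps extends this to 48 h:

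| Share of 4-h gaps | Under 24 h | At most 24 h | Literal 3-hour reading |
|---|---|---|---|
| 0 | 100% | 100% | 100% |
| 1/4 | 96.5% | 99.5% | 38.8% |
| 1/2 | 51.5% | 80.0% | 3.6% |
| 3/4 | 4.7% | 19.4% | under 0.1% |
| 1 | 0% | 0% | 0% |

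In practice repeat doses are optional and may be deferred for non-pharmacologic care, so these chances are upper limits for the given gaps.

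**5. Retention.** 0.8 × 24 = 19.2, so 20 infants are needed: 20/24 = 83.3% meets the criterion and 19/24 = 79.2% does not. If switched infants counted as lost, five switches among the 12 study infants would leave 24 − 5 = 19 and fail it with no other loss. The binomial chance of at least 5 of 12 is 7%, 28% or 56% at an assumed switch probability of 20%, 30% or 40%. If switched infants count as retained, switches have no effect on the criterion.

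**The case against.** Several points on the other side have force.

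- **A 3-hour rhythm may be intended.** Section 7.0 ties scoring to current standard care, Section 5.0 describes the current guideline as 3-hourly, and items 3a and 4 both assume doses 3 hours apart. So it would be wrong to infer that the study-arm steps contain no 3-hour assumption: they do, for dosing. No passage fixes the study-arm scoring interval at 3 hours, however, and Section 7.0 expressly allows 3-4 hours for each group. The conflict is softened but remains.
- **Adherence is monitored.** The calendar in Section 8.0 includes watching for protocol deviations, and Section 13.0 promises monthly reports on adherence. A reader might infer that interval differences are wholly unrecorded; the documents do not support that. But intervals that are not deviations need not appear in such reports, and no passage promises a summary of them.
- **Switching and drop out are listed separately.** Section 3.1 suggests that a switch is not a drop-out, and item 4 speaks of leaving the protocol, whereas Section 11.0 speaks of leaving the study. This makes counting switches as lost the less natural label. It does not define retention, and removal from the protocol can be read the other way.
- **Physician discretion.** Section 11.0 can move an infant whom item 4 misses, so the documents do not support the inference that such an infant cannot be moved. Whether that move counts as switched is left open.
- **Pragmatic design.** In a 24-infant pilot, flexible scoring is legitimate, and finding practical problems is objective 2.2. That favours a light remedy.

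**Conclusion.** The textual conflict stands, with high confidence. Following the plan exactly, an infant scored every 4 hours who qualifies every time never meets item 4. With mixed gaps the rule may fire on time, late or never, depending also on which half of item 4 is applied. The number switched is therefore partly a measure of scoring interval.

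The size of the effect is unknown. The percentages rest on assumed gap shares and on every score leading to a dose. A reader might infer that the rule will seldom fire in this trial; the documents do not support that, since they give no interval data and the unit may score mostly at 3 hours. Nor do they show that the retention criterion will fail because of switches. The failure figures depend on assumed switch probabilities and on a label that the plan does not assign. What stands on retention is that the status of item 4 switches and physician-directed moves is undefined, and that it can decide the only stated success criterion.

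**What to change.** 1. Reconcile Section 5.0 with Section 7.0 (the general scoring paragraph and Study Group items 3a and 4) on the study-arm scoring interval and the switch trigger, including the dose count, the 3-hour wording and whether a dose at exactly 24 h counts. The clinical choice belongs to the clinical team.
2. Before results are seen, state whether item 4 switches and Section 11.0 moves count as switched, dropped out or retained. Report moves to standard dosing by reason: item 4, physician-directed, parent request.
3. Under objective 2.2, summarize actual score-to-score and score-to-dose intervals by arm beside the number switched. Off-window scores can stay non-deviations.

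The cost is a wording clarification, one short definition paragraph, and abstraction of score and dose times for up to 24 infants. Scores are already on the collection list in Section 7.0, and dose data are implied by outcome 3.3, but no passage says that times are captured. The downside is a switch or retention figure that may look less favourable.
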